5. TREATMENT OF SUBJECTS

5.1. Treatment Allocation and Blinding

5.1.1. Randomization, Stratification and Placebo Control

Central randomization will be implemented in this study. Randomization will be used to minimize bias in the assignment of subjects to treatment groups, to increase the likelihood that known and unknown subject attributes (e.g., demographic and baseline characteristics) are evenly balanced across treatment groups, and to enhance the validity of statistical comparisons across treatment groups. Two randomization schemes will be generated: one for each geographic region (North America versus Rest of World). Under each scheme, subjects will be randomized based on the following stratification factors:

- Age 60-69 vs. ≥ 70 years
- FLIPI-1 score at Screening (low vs. intermediate/high)
- ECOG performance status score (0/1 vs. 2)

Subjects will be randomized at a 3:1 ratio to receive either Treatment Arm A (ibrutinib/rituximab) or Treatment Arm B (placebo/rituximab) within each randomization stratum. A placebo control will be used to establish the frequency and magnitude of changes in clinical endpoints that may occur in the absence of active treatment.

Subjects who discontinue study treatment due to any reason other than withdrawal of consent for follow-up will be followed for overall survival. Subsequent anticancer therapies, best response to therapy, and information about other malignancies will be collected.

The interactive voice or web response system (IXRS) will assign a unique treatment code, which will dictate the treatment assignment and matching study treatment kit for the subject. The requestor must use his or her own user identification and personal identification number when contacting the IXRS, and will then provide the relevant subject details to uniquely identify the subject.

5.1.2. Blinding

Blinded treatment will be used to reduce potential bias during data collection and evaluation of clinical endpoints. This is a double-blind study; therefore, subjects, investigators, and the Sponsor's study team members will remain blinded to treatment assignment. The investigator will not be provided with randomization codes.

Data that may potentially unblind the treatment assignment (i.e., study drug plasma concentrations) will be handled with special care to ensure that the integrity of the blind is maintained and the potential for bias is minimized. This may include making special provisions, such as segregating the data in question from view by the investigators, clinical team, or others as appropriate until the time of database lock and/or unblinding.

Under normal circumstances, the blind should not be broken. The blind should be broken only if specific emergency treatment/course of action would be dictated by knowing the treatment status of the subject. In such cases, the investigator may in an emergency determine the identity of the treatment by contacting the IXRS. It is recommended that the investigator contact the sponsor or its designee, if possible, to discuss the particular situation before breaking the blind. Telephone contact with the sponsor or its designee will be available 24 hours per day, 7 days per week. In the event the blind is broken, the sponsor must be informed as soon as possible. The date, time, and reason for the unblinding must be documented in the source documents. The documentation received from the IXRS indicating the code break must be retained with the subject's source documents in a secure manner. A subject whose treatment assignment has been unblinded may continue the study treatment if receiving clinical benefit and the subject should continue to return for scheduled study evaluations. The single-blind (i.e., subject remains blinded to treatment assignment) should be maintained provided the subject's safety is not compromised.

Subjects, investigators, and the sponsor's study team members will remain blinded to treatment assignment until the primary analysis is completed. Examples of personnel who may be unblinded during the study are:

- The independent DMC, and the independent biostatistician and statistical programmers from an independent Statistical Support Group who are responsible for preparing interim tables, listings, and graphs for DMC review. Unblinding procedures and the control of the unblinded data are described in the DMC charter.
- Sponsor's representative responsible for pharmacokinetics testing and analysis.
- Sponsor safety representative to fulfill regulatory reporting requirements for suspected unexpected serious adverse events.

- In case of an urgent safety concern, site personnel and the sponsor may be unblinded, if treatment assignment information is needed to determine further actions to address the urgent safety concern (e.g., life-threatening event, medication error, such as an accidental overdose).

5.2. Study Treatment

- All eligible subjects for randomization will be treated with rituximab in combination with either ibrutinib (Arm A) or matching placebo (Arm B) according to the dose and schedule outlined in [Table 2](#).
- Treatment with ibrutinib or placebo, referred to as study drug, will continue until disease progression, unacceptable toxicity, withdrawal of consent for treatment, or study end, whichever comes first. All subjects treated in this study will follow guidelines for dosing and toxicity management as described in [Section 5.3.1](#) and [Section 5.3.2](#) of the protocol for study drug (ibrutinib/placebo) and rituximab, respectively.

5.2.1. Route and Schedule

Table 2. Treatment, Dose, and Schedule of Administration for Study Treatment

Study Treatment	Dose and Schedule of Administration
Study drug (ibrutinib/placebo)	4 x 140 mg capsules (560 mg ibrutinib or placebo) orally administered daily beginning from Cycle 1, Day 1 (at least 24 cycles).
Rituximab	375 mg/m ² IV per regional prescribing information administered weekly for four consecutive weeks, beginning from Cycle 1, Day 1, followed by maintenance rituximab administered every 8 weeks up to 12 doses (approximately 2 years) beginning Cycle 3, Day 1.
	Rituximab administration days: Cycle 1, Days 1, 8, 15, 22 and Cycle 3, 5, 7, 9, 11, 13, 15, 17, 19, 21, 23 and 25 on Day 1 (a total of 16 doses of rituximab will be given during the study). NOTE: No rituximab will be given in Cycle 2.

5.3. Study Medications

5.3.1. Ibrutinib/Placebo (Study Drug)

For the purposes of this study, study drug refers to both ibrutinib and placebo, the blinded label study drug. All subjects will follow the guidelines for ibrutinib dosing and toxicity management. Ibrutinib/placebo should be administered as described in [Table 2](#) until one or more of the discontinuation criteria in [Section 9.2](#) are met.

5.3.1.1. Ibrutinib/Placebo: Formulation/Packaging/Storage

Ibrutinib capsules are provided as a hard gelatin capsule containing 140 mg of ibrutinib. All formulation excipients are compendial and are commonly used in oral formulations. Refer to the [ibrutinib IB](#) for a list of excipients.

Matching placebo capsules are provided as a hard gelatin capsule and look identical to ibrutinib capsules.

The ibrutinib and placebo capsules will be packaged in opaque high-density polyethylene plastic bottles with labels bearing the appropriate label text as required by governing regulatory agencies. Study drug (ibrutinib/placebo) will be dispensed in child-resistant packaging.

Refer to the Pharmacy Manual/site investigational product manual for additional guidance on study drug storage, preparation and handling.

5.3.1.2. Ibrutinib/Placebo: Dose and Administration

Study drug (ibrutinib/placebo) is recommended to be self-administered on an outpatient basis. Blinded study medication will be administered for continuous daily dosing.

Study drug (4 capsules) is administered orally once daily. The capsules are to be taken around the same time each day with 8 ounces (approximately 240 mL) of water. The capsules should be swallowed intact and subjects should not attempt to open capsules or dissolve them in water. The use of strong CYP3A inhibitors/inducers, and grapefruit and Seville oranges should be avoided for the duration of the study (Section [6.2.1](#) and [Appendix C](#)).

If a dose is not taken at the scheduled time, it can be taken as soon as possible on the same day with a return to the normal schedule the following day. The subject should not take extra capsules to make up the missed dose.

The first dose will be delivered in the clinic on Cycle 1, Day 1, after which subsequent dosing will be self-administered daily by the subjects typically on an outpatient basis. Please refer to [Table 3](#) and Section [8](#) for oral dose and administration instructions on pharmacokinetic visits; on these days, study drug will be administered in clinic as soon as the subject comes into clinic and after pre-dosing procedures. Pre-medications and rituximab will then be administered as outlined in Section [5.3.2.2](#).

Study drug will be dispensed to subjects in bottles. Unused study drug must be returned to the site and drug accountability records (Section [12.8](#)) updated. Returned capsules must not be redispensed to anyone.

Study drug is continuous (without interruptions) throughout the Treatment Phase. If rituximab infusion is delayed due to scheduling conflicts or toxicity, study drug dosing should continue.

Table 3. Study Drug (Ibrutinib/Placebo) Administration

Study Drug	Ibrutinib/placebo
Schedule of Administration	Daily
Route/Regimen	Oral In-clinic dosing days (Cycle 1, Day 1 and 22; Cycle 3, Day 1): supervised by site staff; given as soon as the subject comes into clinic and after pre-dosing procedures. Pre-medications and rituximab will then be administered. Home administration days: self-administered by subject.
Dose	560 mg (4 x 140 mg capsules) or placebo
Dosing Instructions	Take the study drug around the same time each day with approximately 8 ounces of water. Swallow capsules whole (shouldn't open, break, or chew). A missed dose is taken as soon as possible on the same day, with a return to the normal schedule the following day. Extra capsules to make up for a missed dose should not be taken. For days with rituximab scheduled but not in-clinic dosing days as indicated above, take the study drug prior to clinic visit.

COVID-19 Pandemic-Related Direct-to-Patient Shipments

If a subject is unable to come to the study site to pick up their study drug due to COVID-19, study drug may be shipped from the study site directly to the study subject's home via a direct-to-patient (DTP) shipment if the following criteria are met:

- DTP shipment of study drug is allowed by local regulations and the relevant ethics committee
- Subject agrees to have the study drug shipped directly to their home.

Of note:

- Shipments may also include other study supplies (e.g., drug dosing diaries, paper copies of PROs).
- Instructions will be provided by AbbVie as to how a study site can initiate a DTP shipment using Marken, a global vendor selected by AbbVie to provide this service when necessary. Shipments of study drugs from the study site to a subject's home will be appropriately temperature controlled (qualified shipper or temperature monitoring) within the labeled storage conditions. Signature is required upon delivery; due to COVID-19-related social distancing, this may be provided by the courier after delivery. Documentation of the shipment is to be retained by the clinical site.
- AbbVie will not receive subject identifying information related to these shipments, as the site will work directly with the courier.

The study site is responsible for meeting IRB/IEC reporting requirements related to DTP shipments of study drug, and for obtaining consent to provide delivery information to the courier and documenting this consent in source documents.

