5.3.1.4. Ibrutinib/Placebo: Dose Modification for Ibrutinib/Placebo-Related Adverse Reactions

For an ibrutinib/placebo-related adverse reaction, the recommendations for dose modification of ibrutinib/placebo are provided in [Table 4](#) and [Table 5](#) if any of the following hematologic or non-hematologic toxicities occur:

- Grade 3 or greater neutropenia with infection or fever
- Grade 4 neutropenia (ANC<500/ μ L) for more than 7 days. See Section [6.1](#) for instructions regarding the use of growth factor support.
- Grade 3 thrombocytopenia (platelets<50,000/ μ L) in the presence of clinically significant bleeding events.
- Grade 4 thrombocytopenia (platelets<25,000/ μ L).
- Grade 3 or greater non-hematological toxicity (Note: [Table 5](#) recommendations for Grade 3 or higher cardiac failure and cardiac arrhythmias)
- Grade 2 cardiac failure ([Table 5](#))
- Any other Grade 4 or unmanageable Grade 3 hematological toxicity.

If clinically indicated, the use of anticoagulants or antiplatelet agents may be considered for the thromboprophylaxis of atrial fibrillation (Section [6.2.3](#)).

For other grade 3 or 4 AEs, and grade 2 AEs that are deemed per the investigator potentially manageable by dose reduction, these can be managed with a one dose level dose reduction.

In the event that the investigator feels deviation from the recommendations above is required, please consult the Medical Monitor to discuss.

If administration of study drug is delayed or discontinued for toxicity that does not require rituximab to be held for toxicity, rituximab dosing should continue at the investigator's discretion.

Study drug should be discontinued in the event of a toxicity considered to be related to study drug requiring a dose hold lasting more than 28 days, unless reviewed and approved by the Medical Monitor.

Dose changes must be recorded in the Dose Administration eCRF.

Table 4. Ibrutinib/Placebo: Study Drug Dose Modifications for Events not Specified in Table 5

Occurrence	Action to be Taken
First	Withhold study drug until recovery to Grade \leq 1 or baseline; may restart at original dose level (ie, 4 capsules [560 mg/day]) ^a
Second	Withhold study drug until recovery to Grade \leq 1 or baseline; may restart at 1 dose level lower (ie, 3 capsules [420 mg/day])
Third	Withhold study drug until recovery to Grade \leq 1 or baseline; may restart at 1 dose level lower (ie, 2 capsules [280 mg/day])
Fourth	Discontinue study drug

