a. When resuming treatment, restart at the same or lower dose based on benefit risk evaluation. If the toxicity reoccurs, reduce daily dose by 140 mg.

For required dose modification for hepatic impairment refer to Section 5.3.1.5 and for concomitant treatment with CYP3A inhibitors refer to Section 6.2.1. If a subject is being dosed at 280 mg due to hepatic impairment or concurrent CYP3A inhibitor administration, dose level is to be reduced by one capsule to 140 mg at the second occurrence of AEs as described above.

Table 5. Ibrutinib Dose Modifications for Cardiac Failure or Cardiac Arrhythmias

Events	Occurrence	Action
Grade 2 cardiac failure	First	Hold study drug until recovery to Grade \leq 1 or baseline; restart at 1 dose level lower (3 capsules [ie, 420 mg daily])
	Second	Hold study drug until recovery to Grade \leq 1 or baseline; restart at 1 dose level lower (2 capsules [ie, 280 mg daily])
	Third	Discontinue study drug
Grade 3 cardiac arrhythmias	First	Hold study drug until recovery to Grade \leq 1 or baseline; restart at 1 dose level lower (3 capsules [ie, 420 mg daily]) ^a
	Second	Discontinue study drug
Grade 3 or 4 cardiac failure Grade 4 cardiac arrhythmias	First	Discontinue study drug

a. Evaluate the benefit risk before resuming treatment.

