A missed dose of rituximab during the maintenance phase in Cycles 3-25 may be given within the defined visit window (i.e., ± 3 days for Cycle 3 and ± 7 days for Cycles 5-25).

If rituximab dosing is delayed for toxicity that does not require study drug (ibrutinib/placebo) to be held for toxicity, administration of study drug should continue at the investigator's discretion. If a rituximab infusion is delayed due to scheduling delays, administration of study drug should continue.

Any other clinically important events where dose delays may be considered appropriate by the Investigator must be discussed with the Medical Monitor.

Upon recovery, subjects should resume the protocol-specified treatment schedule as soon as possible.

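### Protocol 5.3.1.2 continues study drug through any toxicity-related rituximab delay without condition, which does not agree with 5.3.2.4 or with the hold and stop rules in 5.3.1.4

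*Protocol*

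**What the plan says.** Three parts of the protocol bear on what happens to ibrutinib/placebo when a rituximab dose is delayed.

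- **Section 5.3.1.2 (dose and administration of study drug).** It first says "Study drug is continuous (without interruptions) throughout the Treatment Phase", and then "If rituximab infusion is delayed due to scheduling conflicts or toxicity, study drug dosing should continue". There is no exception and no cross-reference to the modification rules.
- **Section 5.3.2.4 (rituximab dose modification).** It separates the two reasons for delay. After a scheduling delay, study drug continues. After a toxicity delay, the instruction to continue covers only rituximab "delayed for toxicity that does not require study drug (ibrutinib/placebo) to be held for toxicity", and the investigator may decide otherwise.
- **Section 5.3.1.4 (study-drug dose modification).** "For an ibrutinib/placebo-related adverse reaction, the recommendations for dose modification of ibrutinib/placebo are provided in" Tables 4 and 5. The triggers include "Grade 3 or greater non-hematological toxicity" and Grade 4 thrombocytopenia. Table 4 begins with "Withhold study drug until recovery to Grade" 1 or baseline and ends with discontinuation at the fourth occurrence. Table 5, for cardiac failure and arrhythmia, holds or discontinues according to the event and its occurrence.

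**The concern.** A site whose patient has rituximab delayed for toxicity can look up the study-drug instruction in two places and find two answers. Section 5.3.1.2 tells it to continue. Section 5.3.2.4 makes continuation conditional, and 5.3.1.4 may require a hold or a stop. If the toxicity is attributed to both drugs, the literal instructions are opposite.

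The stakes are mainly clarity of clinical management. There is also a reporting side. SAP Section 3.4 summarizes treatment duration, relative dose intensity and dose reductions for adverse events, and SAP Table 7 reports adverse events leading to discontinuation. If sites followed different sections, these summaries would partly reflect which section was read, and protocol compliance could not be judged on one standard.

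**Working it through.** No arithmetic decides this point. The check sets the sections side by side for each reason that rituximab might be delayed.

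| Reason for rituximab delay | 5.3.1.2, read literally | 5.3.2.4 | 5.3.1.4, Tables 4 and 5 | Consistent? |
|---|---|---|---|---|
| Scheduling | Continue | Continue | Not engaged | Yes |
| Toxicity attributed to rituximab only | Continue | Continue, subject to the investigator's judgment | Not engaged (applies to study-drug-related reactions) | Partly: the discretion is missing from 5.3.1.2 |
| Toxicity attributed to both drugs and meeting a 5.3.1.4 trigger | Continue | Its instruction to continue does not apply | Withhold or discontinue | No |

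**Can the third row occur?** Section 5.3.2.4 holds rituximab for related Grade 4 toxicity and for clinically significant, unmanageable non-hematological Grade 3 events. The 5.3.1.4 triggers cover non-hematological toxicity of Grade 3 or above and Grade 4 thrombocytopenia. The thresholds therefore overlap. Sections 1.2.4 and 1.3.2 list arrhythmia, cytopenias, infections and tumor lysis syndrome as risks of both drugs, so dual attribution is foreseeable. Hepatitis B reactivation and progressive multifocal leukoencephalopathy appear under both drugs too, but Section 1.2.4.5 says that causality for ibrutinib has not been established.

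**Is the condition used elsewhere?** Yes. Section 5.3.1.4 has a mirror sentence for the reverse case, study drug delayed for toxicity, and it carries the same type of condition and discretion for rituximab. So the conditional form appears in two sections and is absent from 5.3.1.2. That pattern would fit an omitted qualifier, but the documents do not say so.

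**Does anything rank the sections?** Section 5.2 tells sites to follow 5.3.1 and 5.3.2 for dosing and toxicity management. Section 5.3.1 includes both 5.3.1.2 and 5.3.1.4. Neither statement says which prevails.

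**How many infusions could still be affected?**
- SAP Section 1.3 says enrollment was complete as of July 1, 2021.
- Protocol Table 2 puts the last rituximab dose at Cycle 25 Day 1, with 28-day cycles: (25 − 1) × 28 = 672 days after Cycle 1 Day 1.
- July 1, 2021 plus 672 days is early May 2023 for a last subject on schedule. The visit window (7 days) and the usual limit on a toxicity hold (28 days) move this by weeks.
- The protocol cites an Investigator's Brochure of December 4, 2023, and SAP version 7.0 is dated May 13, 2024. Both are later than that date.

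**The case against.** The strongest reply is that 5.3.1.2 is a general administration paragraph. On this view it says only that a rituximab delay is not in itself a reason to stop study drug, while study-drug toxicity has its own section. The opening of 5.3.1 says that all subjects follow the toxicity management guidelines, Section 9.2 ends treatment for unacceptable toxicity, and several risk paragraphs in 1.2.4 refer sites to 5.3.1.4. Table 5 names its events specifically, and 5.3.1.4 asks for Medical Monitor consultation before its recommendations are departed from.

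Much of this stands. It makes it likely that most sites would apply 5.3.1.4. It also disposes of one tempting reading, that the phrase about continuous dosing forbids any hold. The protocol has holds for severe hepatic impairment (5.3.1.5), CYP3A inhibitors (6.2.1), anticoagulation (6.2.3) and surgery (6.4), so that phrase is better read as describing a daily regimen with no planned off-period.

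The reply does not remove the mismatch. The sentence in 5.3.1.2 is itself specific: it names toxicity as a reason for rituximab delay and says what to do with study drug. It has no qualifier, and nothing ranks it below the others. That 5.3.1.4 presents its actions as recommendations softens the contradiction but leaves it in place.

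**Conclusion.** The inconsistency is real and limited. It concerns toxicity delays only. It is a direct contradiction where one toxicity both delays rituximab and meets a 5.3.1.4 trigger, and a milder difference, over investigator discretion, where the toxicity is attributed to rituximab alone. Section 5.3.2.4 does not itself order a hold; that comes from 5.3.1.4.

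A reader might infer that shared toxicities commonly put subjects under opposite instructions, or estimate a number affected. The documents do not support either. They give no rate of rituximab delay for toxicity and no rate of dual attribution, and a shared list of risks does not show that a single event meets both drugs' thresholds.

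Nor is this a statistical design matter. Alpha, power and sample size are untouched, and SAP Table 2.2 handles premature discontinuation by a treatment-policy strategy, so stopping study drug does not by itself change PFS censoring. The prospective effect is probably small, assuming that the last subjects kept to schedule. Any effect on past infusions depends on whether the same sentence stood in earlier amendments, which the documents do not show.

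**What to change.** Reconcile 5.3.1.2 with 5.3.1.4 (Tables 4 and 5) and 5.3.2.4 so that a subject whose rituximab is delayed for toxicity has one study-drug instruction. Put scheduling delays and toxicity delays in separate sentences, and use identical wording in 5.3.1.2 and 5.3.2.4. The clinical team decides what the rule should be; this review takes no view on it.

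The cost is one sentence in the next amendment or a clarification letter to sites. If no rituximab infusions remain, a note to file would still give one standard for judging compliance and reading the exposure tables. No analysis changes.
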